3.3.2.1 Safety Population – All CXL Treated Eyes

This population consists of study eyes which received the CXL procedure [REDACTED]. In the safety analyses which use this population “baseline” will be when the eye received the CXL procedure.

3.3.2.2 Safety Population – All CXL Treated Patients

This population consists of patients who received the CXL procedure (in either or both eyes). In the safety analyses which use this population a patient’s “baseline” will be the last observation prior to when the patient first receives the CXL procedure in either eye.

3.3.3 Per-Protocol Population

The per protocol (PP) population is a subset of the ITT population and is comprised of study eyes that complete the study without any major protocol deviations and that have non-missing data available for the primary endpoint. The PP population will be used to provide supportive efficacy analyses.

Major protocol deviations include deviations to the inclusion and exclusion criteria, and deviations affecting data integrity as determined by the medical monitor. Subjects with major protocol deviations will be excluded from the PP population and these subjects and their data will be provided in a listing. Patients in the ITT population

who were excluded from the PP population due to major protocol deviations related to COVID-19 will also be indicated.

In the analysis of the PP population study eyes will be analyzed in the treatment group according to the treatment received.

The PP population analyses are supportive analyses.

3.4 ANALYSIS ENDPOINTS

3.4.1 Primary Efficacy Endpoint

The primary efficacy endpoint is the Month 6 change from baseline in K_{max} .

3.4.2 Secondary Efficacy Endpoint

The secondary efficacy endpoint is the Month 12 change from baseline in K_{max} .

[REDACTED]

[REDACTED]

- [REDACTED]
- [REDACTED]
- [REDACTED]

3.4.4 Safety Variables

The primary safety endpoints for this study are:

- Incidence of treatment emergent ocular adverse events
- Loss in BSCVA

[REDACTED]

[REDACTED]

[REDACTED]

The incidence of treatment emergent adverse events will be tabulated presented descriptively.

Additional safety analysis will be performed on the following data:

- Slit lamp biomicroscopy
- Pentacam Pachymetry

- IOP (applanation tonometry)
- Manifest refraction
- Dilated fundus examination
- Endothelial cell count
- Macular OCT

[REDACTED]

3.4.5 Questionnaires

3.4.5.1 National Eye Institute Visual Functioning Questionnaire

Change from baseline to Month 12 in the composite, and each of the vision-targeted subscales on the National Eye Institute Visual Functioning Questionnaire (NEI-VFQ 25) will be summarized by treatment group.

3.5 PATIENT DISPOSITION AND EVALUABILITY

3.5.1 Patient Disposition

Patient disposition (enrollment, randomization, study completion) will be presented for each study eye by treatment group and overall. The number and percentage of study eyes in the ITT, Safety and PP population will be presented. The numbers of study eyes completing and not completing the study, as well as reasons for discontinuations will also be summarized. Patients discontinued for reasons related to COVID-19 will also be indicated.

Additionally, the number of patients/study-eyes assessed at each of the scheduled visits will be summarized by treatment group and overall.

A listing of all patients affected by the COVID-19 related study disruption will be provided by patient ID and by investigational site. The patient listing will include the patient disposition and a description of how the patient's participation was affected.

3.5.2 CXL Treatment by Study Visit

The number of study eyes receiving the CXL procedure will be presented as randomized for the ITT Population by treatment group overall and by site.

The number of study eyes at each scheduled visit will be [REDACTED]

3.5.3 Protocol Deviations

Protocol deviations will be presented in a patient listing by treatment group. Protocol deviations related to COVID-19 will be indicated.

3.6 DEMOGRAPHICS AND BASELINE CHARACTERISTICS

3.6.1 Demographics

Patient demographics and baseline characteristics will be summarized by treatment group and overall for the ITT, Safety Populations, and Per Protocol populations.

Descriptive statistics will be provided for age. Frequencies and percentages will be tabulated for sex, race, and ethnicity. Contact lens use and baseline Keratoconus Severity [REDACTED] will also be summarized:

3.6.2 Medical History

Patient medical history will be presented in patient listings by treatment group.

3.6.3 Ocular History

Patient ocular history will be presented in patient listings.

3.7 EFFICACY ANALYSIS

3.7.1 Primary Efficacy Endpoint Analysis

The primary efficacy endpoint is the Month 6 change from baseline in K_{max} . The primary efficacy null hypothesis is that there is no difference between the CXL Treatment group and the Sham Treatment/Control group in the mean Month 6 change from baseline in K_{max} . The alternative hypothesis is that there is a difference.

The null (H_0) and alternative (H_a) statistical hypotheses for the primary efficacy endpoint, to be tested are:

$$H_0: \mu_T - \mu_C = 0$$

$$H_a: \mu_T - \mu_C \neq 0.$$

Where:

- μ_T is the mean K_{max} change from baseline to 6 months for the CXL Treatment group
- μ_C is the mean K_{max} change from baseline to 6 months for the Sham Treatment/Control group.

[REDACTED]

The primary efficacy analysis will be performed on the ITT population using multiple imputation the main analysis method for handling missing data.

The primary efficacy endpoint criterion is [REDACTED] Month 6 change from baseline in K_{max} between the CXL Treatment group and the Sham Treatment/Control group.

- [REDACTED]
- [REDACTED]
 - [REDACTED]
 - [REDACTED]
 - [REDACTED]
 - [REDACTED]
 - [REDACTED]
 - [REDACTED]

Note: Missing data handling methods are described in Section 3.2.

The primary efficacy analysis will also be performed for patients in the ITT population who were NOT affected by COVID-19 (e.g., Month 6 visit within the visit window). If these results differ from the primary analysis of all patients in the ITT population, the data will be examined to gain an understanding for the difference and additional analyses may be presented.

[REDACTED]

3.7.2 Secondary Efficacy Endpoint Analyses

The secondary efficacy endpoint is the Month 12 change from baseline in K_{max} . The secondary efficacy null hypothesis is that there is no difference in the mean Month 12 change from baseline in K_{max} between the cross-linking treated eyes from this study and the historical control group. The alternative hypothesis is that there is a difference.

[REDACTED]

The secondary efficacy endpoint criterion is [REDACTED] Month 12 K_{max} change from baseline between the CXL Treatment group and the Sham Treatment/control group.

This analysis will be performed on the ITT population as the main analysis using the Month 12 LOCF Method (defined in Section 3.2).

[REDACTED]

- [REDACTED]
- [REDACTED]
- [REDACTED]
- [REDACTED]
- [REDACTED]

Note: Missing data handling methods are described in Section 3.2.

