Post-procedure, eyes will be assessed at Day 1, Day 3, Week 1, Months 1, 3, 6, and 12. Additional clinical visits may be scheduled at the discretion of the Investigator. Pentacam measurements, manifest refraction, Uncorrected Visual Acuity (UCVA), Best Spectacle Corrected Visual Acuity (BSCVA), specular microscopy, dilated fundus examination, Optical Coherence Tomography (OCT) (in a subset of study eyes), and intraocular pressure (IOP) will be obtained at baseline and at the specified times after the treatment. Safety monitoring throughout the study will include observations at appropriate times for AEs, new findings on ophthalmic examination, dilated fundus examination, and slit lamp examination. Quality of vision will be evaluated pre-treatment and post-treatment with a vision related quality of life questionnaire.

Post-procedure follow-up visits and assessments will be contingent on the type of study treatment:

CXL Treatment Group: Post-procedure, study eyes in the CXL Treatment group will be assessed at Day 1, Day 3, Week 1, Months 1, 3, 6, and 12. Additional clinical visits may be scheduled at the discretion of the Investigator.

Sham Treatment/Control Group: Post-procedure, study eyes in the Sham Treatment/Control group will be followed through Month 6 with assessments at Day 1, Day 3, Week 1, Months 1, 3, and 6.

[REDACTED]

[REDACTED]

[REDACTED]

[REDACTED]

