3.2 HANDLING OF MISSING/INCOMPLETE VALUES

Missing data can reduce the statistical power of a study and produce biased estimates leading to invalid conclusions. Therefore, every effort will be made to ensure complete, accurate, and timely data collection, to avoid missing data. Missing clinical outcome data can occur for multiple reasons, including missed subject visits and scales or measures with missing item scores. Missing and incomplete data will be identified for investigation and possible resolution by Data Management prior to the study database lock.

[REDACTED]

Based on a similar study conducted by Avedro, study UVX-002 (*NDA 203-324, UVX-002 Table 14.2.1.1.1*), the percentage of missing data for the Month 6 K_{max} change from baseline endpoint in the CXL group was 8%. It is anticipated the rate of missing data for this study will be similar to the 8% rate for both the CXL and sham treatment groups.

To assess the pattern of missing data, any missing observations for the primary efficacy endpoint will be described in detail and evaluated for assessment of possible bias. For each of the two treatment groups, 95% confidence intervals for the difference in means or proportions stratifying on missing/not-missing the primary endpoint will be performed for the following baseline demographics and characteristics:

- Age
- Sex (female / male)
- Race (white / non-white)
- Ethnicity (Hispanic / non-Hispanic)
- Baseline keratoconus disease severity [REDACTED]

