3.2.1 Multiple Imputation

Multiple imputation will be the method for handling missing data in the primary efficacy endpoint analysis (i.e., the primary endpoint is the Month 6 change from baseline in K_{max}). [REDACTED]

[REDACTED]

The MAR assumption implies that the covariates in the model can account for differences in the distribution of missing variables for observed and missing cases.

[REDACTED]

[REDACTED] However, to assess the robustness of this MAR assumption, multiple sensitivity analyses will be performed, including an analysis which assumes the primary endpoint missing data pattern is Missing Not at Random (MNAR).

[REDACTED]

[REDACTED] The initial imputation to produce a monotonic missing data pattern for the MNAR

imputation will be performed by using the same method as described for the MAR imputation.

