3.2.3 Last Observation Carried Forward

Last Observation Carried Forward (LOCF) will be used for supplemental analysis of the primary efficacy endpoint analysis. For the LOCF analyses, if a study eye is missing the analysis value, the post-baseline value most recent to the missing observation will be imputed for the analysis.

[Redacted text block containing multiple paragraphs of blacked-out content]

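### SAP 3.7.2 makes LOCF the main method for Month 12 Kmax, against multiple imputation at Month 6, so the tested contrast may mix visit times

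*SAP*

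**What the plan says.** **Month 12 (SAP 3.7.2).** The missing-data rule for the secondary endpoint is: "This analysis will be performed on the ITT population as the main analysis using the Month 12 LOCF Method (defined in Section 3.2". SAP 3.7.3 tests this endpoint at two-sided 0.05, with significance conditional on the primary.

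**Month 6 (SAP 3.2.1, 3.2.3 and 3.7.1).** For the same measure six months earlier, "Multiple imputation will be the method for handling missing data in the primary efficacy endpoint analysis". SAP 3.2.1 adds several sensitivity analyses, among them "an analysis which assumes the primary endpoint missing data pattern is Missing Not at Random (MNAR". LOCF has a lesser role: "Last Observation Carried Forward (LOCF) will be used for supplemental analysis of the primary efficacy endpoint analysis".

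**The LOCF rule.** The only visible definition, in SAP 3.2.3, is that "the post-baseline value most recent to the missing observation will be imputed for the analysis". A redacted block follows it. More redacted text follows the LOCF sentence in 3.7.2.

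**Follow-up (Protocol 3.0).** For the active arm, "study eyes in the CXL Treatment group will be assessed at Day 1, Day 3, Week 1, Months 1, 3, 6, and 12". For the control arm, "study eyes in the Sham Treatment/Control group will be followed through Month 6"; the text after the list of sham visits is redacted. SAP 2.2.1 nevertheless counts 80 evaluable sham eyes at Month 12 as well as at Month 6.

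**Comparator (SAP 3.7.2).** The null hypothesis compares treated eyes with a historical control group. The success criterion in the same section compares the CXL group with the sham group.

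**The concern.** The SAP regards LOCF as good enough only for a supplement at Month 6, then relies on it for a formal test at Month 12, where more data are likely to be missing. The visible text gives no reason.

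Carrying forward assumes that Kmax does not change between the last visit and Month 12. In a progressive disease, with a treatment meant to change curvature over time, that assumption is doubtful. A CXL eye last seen at Month 1, 3 or 6 is entered as if measured at Month 12. A sham eye without a later visit is entered at its Month 6 value or an earlier one. If this applies to most of the sham arm, the analysis compares treated eyes at Month 12 with control eyes at Month 6, and any change after Month 6 is confused with a treatment effect.

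At stake is whether the Month 12 result, if significant, can be read as a Month 12 treatment difference.

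**Working it through.** **1. The plan's own figures.** SAP 2.2.1 randomizes 275 eyes as 183 and 92, which is the 2:1 split. Going from 275 to 240 evaluable implies a loss of 1 − 240/275 = 12.7%. The only missing-data rate in the SAP is for Month 6, expected to be "similar to the 8% rate for both the CXL and sham treatment groups". No Month 12 rate is visible, so 8% and 12.7% serve as a range. The design effect and SD are redacted, so the stated power of about 80% can only be solved backwards: (1.96 + 0.84) × √(1/160 + 1/80) = 0.384 SD. This is not an independent check, and the results below are therefore in SD units.

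**2. Interval width.** Suppose a fraction m is missing at Month 12 in both arms, data are normal and missing at random, the SDs at Months 6 and 12 are equal, and the two changes have correlation ρ. Then

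SE(LOCF) / SE(MI) = 1 / √[1 + m(1 − ρ²)/(1 − m)].

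| m | ρ = 0.5 | ρ = 0.7 | ρ = 0.9 |
|---|---|---|---|
| 8% | 0.969 | 0.979 | 0.992 |
| 12.7% | 0.950 | 0.965 | 0.986 |

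For example, 0.08 × 0.75/0.92 = 0.0652, and 1/√1.0652 = 0.969. LOCF intervals are about 1-3% narrower at 8% and up to about 5% narrower at 12.7%. If only CXL eyes are missing, the effect shrinks further. The CXL arm supplies (1/183)/(1/183 + 1/92) = 0.335 of the variance, so the largest reduction at 12.7% is 1 − 1/√(1 + 0.335 × 0.109) = 1.8%.

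In a 20,000-replicate simulation (183 against 92 eyes, ρ = 0.7, 8% missing in each arm, the same drift in both arms and no true effect), the test rejected in 4.8-5.1% of trials. The model SE matched the empirical SD (0.128 and 0.128).

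**3. Carried CXL values.** The shift in the CXL mean is m times the average gap between the carried value and the true Month 12 value. With an assumed gap of 0.5 to 1.0 D, it runs from 0.08 × 0.5 = 0.04 D to 0.127 × 1.0 = 0.13 D.

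**4. All sham values carried from Month 6.** This is the extreme case suggested by the visible follow-up text. Suppose both arms drift by g after Month 6, there is no true effect, and 8% of CXL eyes are also carried. The expected false difference is (1 − 0.08)g, with SE √(1/183 + 1/92) = 0.128 SD.

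| g (SD, assumed) | False difference, 0.92g | Rejection (simulated) | 95% CI coverage |
|---|---|---|---|
| 0.1 | 0.09 | 11% | 89% |
| 0.2 | 0.18 | 30% | 70% |
| 0.3 | 0.28 | 58% | 42% |

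With steepening in both arms (g positive), the false difference goes against CXL. With flattening in both arms, it favours CXL: g = −0.1 and −0.2 give rejection of 11% and 30%.

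If instead sham eyes go on worsening and CXL eyes are stable, carrying forward understates the benefit by the amount of the worsening. Coverage of the true Month 12 difference is then 88%, 65% and 35% for worsening of 0.1, 0.2 and 0.3 SD.

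**The case against.** **Redaction.** SAP 3.7.2 cites a named method, and the text that would define it, justify it or add Month 12 sensitivity analyses may be blacked out in 3.2.3 or 3.7.2. A reader might infer that the SAP has no Month 12 imputation or MNAR analysis. The documents do not show that; they show only that none is visible. This stands as a limit on the point.

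**LOCF may be deliberate for sham eyes.** In the earlier trials, according to the note to Figure 1 in Protocol 1.0, the last Kmax before later cross-linking was used for sham eyes at subsequent time points. A similar convention may apply here. Multiple imputation could not replace it: if no sham eye has an untreated Month 12 value, the imputation model has no sham data at that visit to learn from. This also stands. It does not explain LOCF for CXL eyes, which are followed to Month 12 and have Kmax at Months 1, 3 and 6 (SAP 2.2.4.1).

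**Precision.** A reader might infer that LOCF makes the intervals seriously too narrow. That comes from treating carried values as having no information about Month 12 and from applying a one-arm reduction to a two-arm difference. Step 2 shows an effect of a few percent, with type I error near 5% when missingness and drift are alike in both arms.

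**Earlier sham results.** It is tempting to halve the 0.5-0.6 D sham increases reported in Protocol 1.0 and call the result the progression missed after Month 6. Those Month 12 means were themselves partly carried forward, so they are not observed 12-month progression and cannot be scaled in that way.

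**Comparator.** If the test is against a historical control, the sham argument in step 4 no longer applies. The argument about carried CXL values does.

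**Conclusion.** The change of method between Months 6 and 12 is real and has no visible explanation, and it affects an endpoint tested formally at 0.05. The primary endpoint is not affected.

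The weight of the point is on bias from mixed visit times. For CXL eyes the bias is modest: 0.04-0.13 D under the assumed gap and the 8-12.7% range. For the contrast with sham it could be large: with every sham value carried, drifts of 0.1-0.3 SD bring rejection to 11-58% with no true effect. That case is an inference from the visible sham follow-up. SAP 2.2.1 points the other way by counting 80 evaluable sham eyes at Month 12, and the deciding text is redacted. The drift, SD and correlation are all assumptions.

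A reader might infer that LOCF flatters the treatment. The documents do not support a fixed direction: it depends on how each arm changes after Month 6, and continued sham worsening would understate the benefit. The effect on interval width is minor.

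**What to change.** In SAP 3.7.2:

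- Make the multiple imputation of SAP 3.2.1, extended to Month 12 with the same MNAR sensitivity analysis, the main method for missing CXL Kmax at Month 12. Move LOCF to supplemental, as for the primary.
- Reconcile the comparator, so that the null hypothesis and the success criterion both name sham or both name the historical control.
- If the comparator is sham, report carried sham values as Month 6 values and not as Month 12 estimates. Add a sensitivity analysis over a stated range of sham drift after Month 6. Imputing CXL eyes alone does not repair this comparison.
- If redacted text already covers any of this, refer to it from 3.7.2.

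The cost is SAP wording, one more visit in the existing imputation, one extra sensitivity analysis and a slightly wider interval. No new data are needed.

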3.7.3 Control of Type I Error Rate

Both the primary and secondary efficacy endpoint (K_{max} change from baseline at Months 6 and 12, respectively) are tested at the two-sided 0.05 Type I error rate. The secondary efficacy endpoint analysis will only be considered statistically significant if the primary efficacy endpoint analysis is statistically significant.

[REDACTED]

[REDACTED]

- [REDACTED]

[Redacted text block containing multiple paragraphs of obscured content]

[REDACTED]

3.8 SAFETY ANALYSIS

All safety analyses will be performed on the Safety Population.

[REDACTED]

3.8.2 Adverse Events

Treatment Emergent adverse events (TEAEs) will be summarized by treatment group and categorized by system organ class (SOC) and preferred term (PT) using the Medical Dictionary for Drug Regulatory Affairs (MedDRA 15.1 or higher). TEAEs are adverse events (AEs) which occurred after study treatment administration or pre-existing AEs that worsened after study treatment administration.

The number and percentage of subjects reporting non-ocular AEs will be tabulated by body system and preferred term within each treatment and overall. The number and percentage of study eyes reporting ocular AEs will be tabulated by preferred term

within each treatment group and overall. The number of subjects/study eyes reporting AEs will also be summarized by relationship to the test article as well as severity of AEs. Serious adverse event (SAEs) will also be summarized by group and categorized by SOC and PT. An AE with a relationship to the test article of Possible, Probable, or Definite will be considered “Related”.

AEs will be summarized over the following time periods based on the onset date of the TEAE:

- Baseline to Month 3: TEAEs with an onset date up to and including the Month 3 visit
- Baseline to Month 6: TEAEs with an onset date up to and including the Month 6 visit
- Study Period: All TEAEs.

For the presentation of AE incidences, the SOCs will be sorted alphabetically, and within SOC, the preferred term (PT) will be used and presented by decreasing total frequency.

The incidence of serious ophthalmic adverse events will be summarized by treatment group and presented in a listing.

Ocular and non-ocular AEs will be summarized separately. Each of these adverse event summaries will be provided for:

- Non-ocular AEs (Subject Level):
 - [Redacted]
 - [Redacted]
- Ocular adverse events (Study Eye Level):
 - [Redacted]

- [REDACTED]
- [REDACTED]

3.8.2.1 Timing and Duration of Frequent Adverse Events

The timing of onset day, resolution day, and duration of TEAEs with an incidence >5% (i.e., > 5% in the CXL Treatment study eyes) will be summarized. This will include TEAE onset day, Resolution day, and Duration (in days).

3.8.3 BSCVA and UCVA

For the safety analysis, BSCVA and UCVA will be presented in terms of the number of ETDRS letters lost/gained or not changed from baseline by each treatment group.

- [REDACTED]
- [REDACTED]
- [REDACTED]
- [REDACTED]
- [REDACTED]
- [REDACTED]
- [REDACTED]
- [REDACTED]
- [REDACTED]

3.8.4 Slit Lamp Biomicroscopy and Dilated Fundus Examination

Slit lamp biomicroscopy and dilated fundus examination data will be presented categorically (i.e., normal/abnormal) at baseline and each of the follow-up visits by treatment group. The following sites are assessed for slit lamp:

- Orbit/Lids
- Lashes

- Pupil
- Conjunctiva
- Cornea-Epithelium
- Cornea-Descemet's Membrane/Endothelium
- Corneal Clarity
- Cornea (Other)
- Anterior Chamber
- Iris
- Lens

The following are the assessments from the dilated fundus exam:

- Lens
- Macula
- Retinal Vessels
- Peripheral Retina
- Optic Disc
- Cup/Disc Ratio.

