In Studies UVX-001 and UVX-002, the average age of keratoconus subjects was 33 years and the average baseline maximum corneal curvature (K_{max}) was 61 diopters (D). At Month 12 in study UVX-001, the CXL treated keratoconus eyes had an average K_{max} reduction of 1.4 D compared to an average increase in K_{max} of 0.5 D in the sham treated eyes for a difference of 1.9 D between the treatment groups. In study UVX-002 at Month 12, the CXL treated eyes had an average K_{max} reduction of 1.7 D compared with an average increase in K_{max} of 0.6 D in the sham treated eyes for a difference of 2.3 D between the treatment groups (see **Figure 1**).

Figure 1: Mean Change from Baseline K_{max} in Patients with Progressive Keratoconus (UVX-001, UVX-002)

Post-baseline missing data were imputed using last available K_{max} value. For the sham study eyes that received the cross-linking treatment after baseline, the last K_{max} measurement recorded prior to receiving cross-linking treatment was used in the analysis at later time points.

In progressive keratoconus subjects, the most common ocular adverse reactions in any CXL-treated eye were corneal opacity (haze), punctate keratitis, corneal striae, corneal epithelium defect, eye pain, reduced visual acuity, and blurred vision. These events are expected sequelae following epithelial corneal debridement and occurred at a higher incidence than observed in control (sham group) subjects, who did not undergo debridement or UV exposure. The majority of adverse events reported resolved during the first month, while events such as corneal epithelium defect, corneal striae, punctate keratitis, photophobia, dry eye, and eye pain, and decreased visual acuity took up to 6 months to resolve. Corneal opacity or haze took up to 12 months to resolve. In 1-2% of subjects, corneal epithelium defect, corneal edema, corneal opacity and corneal scar continued to be observed at 12 months.

US Clinical Studies of Epithelium-off Corneal Cross-linking

Studies KXL-001 and KXL-002 were Phase 3, multi-center, randomized, placebo-controlled studies of the safety and efficacy of high power/accelerated corneal collagen cross-linking performed with UVA irradiation and riboflavin ophthalmic solution in eyes with keratoconus. In these studies, the cross-linking was performed after removal of the epithelium (i.e., epithelium off) and the cornea irradiated continuously for 4 minutes. These studies are completed and data analysis is in progress.

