The slit lamp exam conducted by the Investigator should include a complete survey of the anterior segment including orbit/lids, lashes, pupil, conjunctiva, cornea, anterior chamber, iris, and lens. A grading of normal or abnormal will be noted at each visit. The following areas of the cornea should be examined – Epithelium, Descemet's membrane/endothelium, cornea-other. The grading of any abnormalities in any of the above mentioned areas should be recorded using the following scale:

0+ = 
1+ = 
2+ = 
3+ = 
4+ = 

In addition, the corneal clarity should be examined in detail with specific recordings and grading of any abnormalities using the following scale:

- 0+ = [REDACTED]
- 1+ = [REDACTED]
- 2+ = [REDACTED]
- 3+ = [REDACTED]
- 4+ = [REDACTED]

[REDACTED]

PENTACAM TOPOGRAPHY

[REDACTED] The median K_{max} value is to be reported in the eCRF. [REDACTED]

[REDACTED]

[REDACTED]

[REDACTED]

- [REDACTED]
- [REDACTED]
- [REDACTED]
 - [REDACTED]
 - [REDACTED]
 - [REDACTED]
 - [REDACTED]
 - [REDACTED]
 - [REDACTED]

SPECULAR MICROSCOPY

The methods used for the collection and analysis of specular microscopy data are critically important to minimizing the variability associated with these measurements. Common sources of variability in specular microscopy are:

- difficulty in returning to same location on the cornea at each visit;
- poor image quality (less than 100 countable cells);
- technician error

An acceptable image has:

- distinct cells;
- at least 100 identifiable (countable) cells as a minimum, 150 cells preferred; and
- cells that can be grouped in a uniform area.

To capture a good image:

- make sure the subject is comfortable;
- instruct the subject to blink;
- instruct subject not to move and to open eyes wide;
- instruct subject to focus straight ahead or on the green light;
- be patient; and
- if necessary, use the manual setting. (Note that the use of the manual setting may require additional training).

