3.1.2 Reporting of Numerical Values

All clinical study data will be presented in patient data listings. Descriptive statistics (n, mean, standard deviation, median, minimum, and maximum) will be calculated by treatment group for continuous variables. Descriptive statistics for categorical variables will include number and percentage of subjects or eyes, as appropriate. Confidence intervals will be provided where appropriate.

Means, medians, and confidence intervals will be reported to one decimal place. Standard deviations will be reported to two decimal places. Minimum and maximum will be reported to the same number of decimal places displayed on the Case Report/Record Form (CRF) or by the laboratory/vendor. P-values will be reported to 4 decimal places.

All testing and confidence intervals will use a two-sided significance level of 5% unless otherwise specified.

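### SAP 3.8.4 tabulates slit lamp findings only as normal/abnormal although sites record 0+ to 4+ grades, so the table cannot show severity, worsening or partial recovery of corneal findings

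*SAP*

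**What the plan says.** **Collection.** Protocol Appendix A (Slit Lamp Exams) asks for three things:
- a binary call: "A grading of normal or abnormal will be noted at each visit";
- a grade: "The grading of any abnormalities in any of the above mentioned areas should be recorded using the following scale", with levels 0+ to 4+;
- a separate corneal assessment: "the corneal clarity should be examined in detail with specific recordings and grading of any abnormalities using the following scale", again with levels 0+ to 4+.

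The wording of the grades on both scales is redacted.

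**Reporting.** SAP 3.8.4 states: "Slit lamp biomicroscopy and dilated fundus examination data will be presented categorically (i.e., normal/abnormal) at baseline and each of the follow-up visits", by treatment group. Its list of slit lamp sites includes "Corneal Clarity", separately from the epithelium, Descemet's membrane/endothelium and other-cornea items. The section mentions no grade frequencies, worst grade or shift from baseline, and shows no redaction.

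**Other routes.** SAP 3.1.2 says "All clinical study data will be presented in patient data listings". SAP 3.8.2 counts as treatment-emergent any "pre-existing AEs that worsened after study treatment administration". It tabulates ocular events per study eye by arm and summarises events by severity and relationship. SAP 3.8.2.1 adds onset, resolution and duration for events above 5% in CXL eyes.

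**The concern.** The protocol collects an ordinal measure of corneal findings, and the section of the SAP devoted to it discards the order. A binary table by visit answers how many eyes are abnormal. It does not say how abnormal they are, or whether an individual eye is better or worse than at its own baseline.

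Corneal clarity matters for this treatment. Protocol 1.0 lists corneal opacity (haze) first among the common ocular reactions in the earlier keratoconus trials of cross-linking and adds: "Corneal opacity or haze took up to 12 months to resolve". A finding that comes on and then fades over months is the kind whose course a grade can describe and a yes/no call cannot. What is at stake is how clearly the report describes corneal safety by arm. The efficacy claim is not involved.

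**Working it through.** The plan gives no figure to reproduce here, so the check compares what is collected with what is tabulated.

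**1. What a two-category table retains.** Inputs: five levels, 0+ to 4+ (Protocol Appendix A); two categories (SAP 3.8.4). Assumption: 0+ corresponds to normal and 1+ to 4+ to abnormal. The redacted definitions prevent confirmation.
- Possible upward moves between two levels: 5 × 4 / 2 = 10.
- Moves that cross from normal to abnormal, and so change the table: 1 × 4 = 4.
- Moves within the abnormal range, which leave it unchanged: 4 × 3 / 2 = 6.

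By symmetry, six of the ten downward moves are also invisible. This counts types of move and says nothing about how often each occurs.

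**2. The three things lost.**
- *Severity of a new finding.* A normal eye that becomes 1+ and one that becomes 4+ add the same single count.
- *Worsening in an abnormal eye.* A move from 1+ to 4+ is abnormal at both visits.
- *Partial recovery.* An eye that falls from 3+ to 1+ also shows no change, so the course of a finding after treatment is blurred until it clears completely.

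In addition, frequencies by visit do not pair an eye with its own baseline, so new and resolved abnormalities can offset each other.

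**3. What the other routes add.**

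| Route | What it gives | What it does not give |
|---|---|---|
| Listings (SAP 3.1.2) | Recorded data, eye by eye | A summary by arm and visit |
| Adverse event tables (SAP 3.8.2) | Events per eye by arm, including worsened pre-existing ones, and a severity summary | Corneal grade: Protocol 9.2 rates severity by how well the subject tolerates the event, need for therapy and effect on daily life |
| Event timing (SAP 3.8.2.1) | Onset, resolution and duration | Grade over time, or events at or below 5% in CXL eyes |

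**4. Consistency within the SAP.** Other safety measures are summarised as change from baseline: letters gained or lost (3.8.3), pachymetry (3.8.5), refraction (3.8.7), topography (3.8.8) and endothelial cells as percent change (3.8.9). The graded corneal findings are given no measure of change in the section that covers them.

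**The case against.** The strongest reply is that the SAP as a whole already covers worsening. Much of that stands. Adverse events may be any unfavourable sign (Protocol 9.0), those the investigator observes are to be recorded, and Protocol 9.7 asks for any adverse event to be reported. Recording calls for clinical judgement but is not optional. A reader might infer that worsening haze would go unreported by arm; the documents do not support that. What the reply does not supply is a summary on the corneal scale itself.

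A reader might also infer that the grades are summarised nowhere. That cannot be established. Text is redacted in SAP 3.4.4, 3.8 and 3.8.2 and in Protocol 10.8; after one sentence of SAP 3.8 the next visible subsection is 3.8.2. A graded display could sit in any of these places. The finding is confined to 3.8.4, which reads as complete.

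Two further inferences go too far:
- *That corneal clarity is usually abnormal at entry because every eye has keratoconus.* Protocol 1.0 describes the disease as thinning and steepening, SAP 3.8.4 lists clarity apart from the other corneal sites, and no baseline rate is given. If clarity is normal at entry, new haze does appear in the table and only its grade is lost.
- *That haze will be as frequent here as before.* The background data come from epithelium-off treatment, and Protocol 1.0 attributes the listed reactions to debridement. Its 1-2% of subjects with findings at 12 months covers four findings together.

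Finally, the normal/abnormal call is itself collected at each visit, and slit lamp data are an additional safety analysis (SAP 3.4.4), not a primary safety endpoint. Both are true, and they limit the weight of the point.

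**Conclusion.** The point holds for the table in SAP 3.8.4. As specified, it cannot show the severity of a new corneal finding, worsening in an eye that is already abnormal, or partial recovery. The adverse event tables and listings compensate only in part. The conclusion follows from the table's design and needs no assumed event rate.

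Its size in eyes cannot be stated: the documents give neither baseline abnormality rates nor expected shifts in grade. The count of six hidden moves out of ten rests on reading 0+ as normal. That haze is recorded under corneal clarity is also an inference, because the grade definitions are redacted. This is a gap in descriptive safety reporting. It changes no planned hypothesis test.

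**What to change.** Keep the normal/abnormal table in SAP 3.8.4. For Corneal Clarity and each of the other corneal sites, add:
1. the number and percentage of eyes at each grade, by visit and arm;
2. a shift table from baseline at each follow-up visit, by arm, with the number and percentage of eyes worse by at least 1 grade and by at least 2 grades.

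If a redacted section already specifies such a display, a cross-reference from 3.8.4 is enough.

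The cost is SAP wording and a few extra descriptive tables. Appendix A already requires the grades, and Protocol 11.2 puts all study data on the eCRF, so no new visits or data collection are needed.
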